## 7 DISCONTINUATION OF STUDY INTERVENTION AND PARTICIPANT WITHDRAWAL

### 7.1 Discontinuation of Study Intervention

Discontinuation of study intervention does not represent withdrawal from the study.

As certain data on clinical events beyond study intervention discontinuation may be important to the study, they must be collected through the participant's last scheduled follow-up, even if the participant has discontinued study intervention. Therefore, all participants who discontinue study intervention prior to completion of the protocol-specified treatment period will still continue to participate in the study as specified in Section 1.3 and Section 8.11.4.

Participants may discontinue study intervention at any time for any reason or be discontinued from the study intervention at the discretion of the investigator should any untoward effect occur. In addition, a participant may be discontinued from study intervention by the investigator or the Sponsor if study intervention is inappropriate, the study plan is violated, or for administrative and/or other safety reasons. Specific details regarding procedures to be performed at study intervention discontinuation are provided in Section 8.1.10.

A participant must be discontinued from study intervention but continue to be monitored in the study for any of the following reasons:

- The participant or participant's legally acceptable representative requests to discontinue study intervention.
- The participant has a medical condition or personal circumstance which, in the opinion of the investigator and/or Sponsor, placed the participant at unnecessary risk from continued administration of study intervention.
- The participant has a confirmed positive serum pregnancy test.
- Consecutive (2 or more measurements within 1 week) elevations in ALT or AST  $\geq 3 \times$  ULN.

- Consecutive(2 or more measurements within 1 week) elevations in CK  $\geq 10$  x ULN with or without muscle symptoms.
- Consecutive (2 or more measurements within 1 week) elevations in CK  $\geq 5$  to  $< 10$  x ULN with muscle symptoms.
- The participant is requiring any treatment with telaprevir or fibrates.
- The participants are requiring any treatment with a potent inhibitor of cytochrome P450 3A4 (CYP3A4) such as, itraconazole, ketoconazole, erythromycin, clarithromycin or HIV protease inhibitors for their emerging medical conditions.

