### 8.3.4 Clinical Safety Laboratory Assessments

Refer to Appendix 2 for the list of clinical laboratory tests to be performed and to the SoA for the timing and frequency.

- The investigator or medically qualified designee (consistent with local requirements) must review the laboratory report, document this review, and record any clinically relevant changes occurring during the study in the AE section of the case report form (CRF). The laboratory reports must be filed with the source documents. Clinically significant abnormal laboratory findings are those which are not associated with the underlying disease, unless judged by the investigator to be more severe than expected for the participant's condition.
- All protocol-required laboratory assessments, as defined in Appendix 2, must be conducted in accordance with the laboratory manual and the SoA.
- If laboratory values from nonprotocol specified laboratory assessments performed at the institution's local laboratory require a change in study participant management or are considered clinically significant by the investigator (eg, SAE or AE or dose modification), then the results must be recorded in the appropriate CRF (eg, SLAB).
- For any laboratory tests with values considered clinically significantly abnormal during participation in the study or within 14 days after the last dose of study intervention, every attempt should be made to perform repeat assessments until the values return to normal or baseline or if a new baseline is established as determined by the investigator.

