#### **8.4.7 Events of Clinical Interest (ECIs)**

Selected nonserious and SAEs are also known as ECIs and must be reported to the Sponsor.

Events of clinical interest for this study include:

1. An elevated AST or ALT lab value that is greater than or equal to 3X the upper limit of normal and an elevated total bilirubin lab value that is greater than or equal to 2X the upper limit of normal and, at the same time, an alkaline phosphatase lab value that is less than 2X the upper limit of normal, as determined by way of protocol-specified laboratory testing or unscheduled laboratory testing.\*

\*Note: These criteria are based upon available regulatory guidance documents. The purpose of the criteria is to specify a threshold of abnormal hepatic tests that may require an additional evaluation for an underlying etiology. The study site guidance for assessment and follow-up of these criteria can be found in the Investigator Study File Binder (or equivalent).

2. An overdose of Sponsor's product, as defined in Section 8.5, that is not associated with clinical symptoms or abnormal laboratory results.
3. Myopathy, rhabdomyolysis, or if the CK criterion necessitating study medication discontinuation is met, the event should be reported as ECI because of their association with lipid-lowering treatments.

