### **8.11.3 Treatment Period (Visit 4-Visit 6)**

After 5-week run-in treatment, participants who archive  $\geq 75\%$  compliance with the run-in medication and have not met their treatment goals for LDL-C according to their risk levels will be eligible for study entry. The site will perform all procedures for Visit 4 and the participant will be randomized. After the all procedures have been completed, the study drugs will be dispensed and the participants should take the treatment at a consistent time each day to promote compliance.

The following visits will be scheduled every 6 weeks for participants to return to perform the study procedures required as per Section 1.3 – SoA.

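### The two CK stopping rules in Section 7.1 miss a symptomatic participant whose only two CK values in the week fall either side of 10 x ULN

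*Combined protocol and SAP*

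**What the plan says.** Section 7.1 lists reasons for which study intervention has to be stopped while follow-up continues. Two concern CK.

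- The first begins "Consecutive(2 or more measurements within 1 week) elevations in CK", sets the level at 10 x ULN or more, and applies "x ULN with or without muscle symptoms".
- The second has the same repeat requirement and covers "elevations in CK $\geq 5$ to $< 10$ x ULN with muscle symptoms".

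The same list has a judgement-based reason: a condition or circumstance that "in the opinion of the investigator and/or Sponsor, placed the participant at unnecessary risk". Section 7.1 also lets the investigator stop treatment for any untoward effect.

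Section 8.4.7, item 3, ties ECI reporting to the stopping rule: "Myopathy, rhabdomyolysis, or if the CK criterion necessitating study medication discontinuation is met, the event should be reported as ECI".

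On the timing of CK measurements, Section 8.11.3 states: "The following visits will be scheduled every 6 weeks for participants to return". For clinically significant abnormal results, Section 8.3.4 says that "every attempt should be made to perform repeat assessments until the values return to normal or baseline", or until a new baseline is established. It sets no interval between repeats.

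**The concern.** Because the second criterion is capped below 10 x ULN, a value of 15 x cannot count towards it, and a single value of 15 x cannot satisfy the first. A symptomatic participant with one value in each band therefore meets neither. The rule then asks for less when CK is higher: 15 x and 9 x both exceed 6 x, yet only the 6 x/6 x pair must stop.

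At stake are the objective muscle-safety stop and the ECI report linked to it. Under Table 5 in Section 8.4.1, an ECI reaches the sponsor within 5 calendar days, or 24 hours if it requires regulatory reporting. A nonserious adverse event follows only the data entry guidelines. Muscle events are an adverse event of interest in Section 4.2.1.2, and the synopsis shows no data monitoring committee, so site-level rules carry more of the load.

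**Working it through.** **Inputs.** The thresholds and the repeat requirement come from the two CK criteria in Section 7.1. The number randomized (450) comes from Section 9.9. The documents state no figure for this point, so there is none to reproduce first.

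**Definitions.** Let L be a CK value from 5 to below 10 x ULN and H a value of 10 x ULN or more. Muscle symptoms are present. As in the protocol's own parenthesis, *consecutive* is taken to mean at least two values within one week.

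**Two values of at least 5 x ULN**

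| Order | First criterion (two H) | Second criterion (two L) | Mandatory stop |
|---|---|---|---|
| L, L (6 x, 6 x) | no | yes | yes |
| H, H (15 x, 15 x) | yes | no | yes |
| H, L (15 x, 9 x) | no | no | **no** |
| L, H (8 x, 12 x) | no | no | **no** |

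So 2 of 4 ordered combinations are missed.

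**Three values of at least 5 x ULN.** Three values in two bands always put at least two in one band, so 0 of 8 orders are missed. If a site instead reads *consecutive* as adjacent, H-L-H and L-H-L have no adjacent pair in one band, and 2 of 8 are missed.

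**Is a third value assured?** With treatment visits 6 weeks apart, a week contains at most one scheduled on-treatment value. The second and third are both unscheduled repeats, and Section 8.3.4 does not say how soon to take them.

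**How much CK must move for the pair to straddle 10 x ULN**

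- First value 15 x: a fall of more than 1 − 10/15 = 33.3% and up to 1 − 5/15 = 66.7%.
- First value 12 x: a fall of more than 1 − 10/12 = 16.7% and up to 1 − 5/12 = 58.3%.
- First value 8 x: a rise of 10/8 − 1 = 25.0% or more.
- First value 9 x: a rise of 10/9 − 1 = 11.1% or more.

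**Could the gap be a deliberate allowance for falling CK?** No. A symptomatic fall from 9.9 x to 5 x (1 − 5/9.9 = 49.5%) must stop. A smaller proportional fall from 15 x to 9 x (1 − 9/15 = 40.0%) need not. The rising pair 8 x then 12 x is also missed.

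**Effect of removing the cap.** Both versions of the rule were applied to every ordered pair from 1 to 30 x ULN in steps of 0.5. With symptoms, 820 pairs change from no stop to stop. Every one has one value in L and one in H: 2 orders × 10 values in L × 41 values in H = 820. Without symptoms, no outcome changes. After the change, 0 of the 4 two-value combinations are missed.

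**Number of people.** The documents give no CK event rate. If 0.1% to 1% of those randomized had a symptomatic pair at or above 5 x ULN (assumption), that is 450 × 0.001 = 0.45 to 450 × 0.01 = 4.5 people. Only the straddling part of these is affected, and the documents give no basis for that fraction.

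**The case against.** The strongest reply is that no competent investigator would leave a symptomatic participant with 15 x then 9 x ULN on treatment. The unnecessary-risk reason is itself mandatory once the opinion is formed. The investigator sees CK results, may stop for any untoward effect, and may use a local laboratory. Myopathy and rhabdomyolysis are ECIs in their own right. This all stands and makes serious harm unlikely, but it replaces an automatic threshold with judgement in a place where the protocol chose to have both.

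The guideline reproduced in Appendix 7 (Section 10.1.1 of that guideline) advises reducing or stopping the statin when muscle complaints accompany progressively rising CK, and Section 6.6 plans no dose modification. That points towards stopping for a rising pair. It is reproduced guidance rather than a trial stopping criterion, and it does not reach the falling pair.

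Two further points narrow the contrast. Even the 6 x/6 x stop depends on someone ordering a retest within the week. Section 8.1.10 also allows treatment to be restarted after discontinuation. Both reduce the practical difference between a pair that triggers the rule and one that does not. Neither explains why the higher pair should be treated less strictly.

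Finally, the three-value result depends on how *consecutive* is read. The reading used here follows the protocol's parenthesis; the alternative only widens the gap.

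**Conclusion.** The concern holds. As written, the automatic CK rule is not monotone, and the CK-based ECI trigger has the same gap. The result is exact given the stated thresholds. It is limited to symptomatic participants with exactly two CK values of at least 5 x ULN in the week, one on each side of 10 x ULN.

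Very few people are likely to be affected, possibly fewer than one; the headcount rests entirely on an assumed event rate. Efficacy, power and multiplicity are untouched. Table 7 needs no correction, because its symptomatic endpoint at 5 x ULN or more has no upper limit and already counts these cases. The change is worth making because a stated safety rule gives the wrong answer and the correction is nearly free, but it is not critical to the trial's validity.

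**What to change.** In the second CK criterion of Section 7.1, delete the upper limit (*to <10*), so that it applies to two or more values within one week at ≥5 x ULN with muscle symptoms. Keep the criterion at 10 x ULN or more, which applies regardless of symptoms, as it is. Section 8.4.7, item 3, then follows through its existing reference to the stopping criterion, and the wording matches the uncapped endpoint in Table 7. The cost is one deletion in one bullet, with no added tests, visits or participants.

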## 7.2 Participant Withdrawal From the Study

A participant must be withdrawn from the study if the participant or participant's legally acceptable representative withdraws consent from the study.

If a participant withdraws from the study, they will no longer receive study intervention or be followed at scheduled protocol visits.

Specific details regarding procedures to be performed at the time of withdrawal from the study, are outlined in Section 8.1.10. The procedures to be performed should a participant repeatedly fail to return for scheduled visits and/or if the study site is unable to contact the participant are outlined in Section 7.3.

## 7.3 Lost to Follow-up

If a participant fails to return to the clinic for a required study visit and/or if the site is unable to contact the participant, the following procedures are to be performed:

- The site must attempt to contact the participant and reschedule the missed visit. If the participant is contacted, the participant should be counseled on the importance of maintaining the protocol-specified visit schedule.

- The investigator or designee must make every effort to regain contact with the participant at each missed visit (eg, telephone calls and/or a certified letter to the participant's last known mailing address or locally equivalent methods). These contact attempts should be documented in the participant's medical record.
- Note: A participant is not considered lost to follow-up until the last scheduled visit for the individual participant. The missing data for the participant will be managed via the prespecified statistical data handling and analysis guidelines.

## 8 STUDY ASSESSMENTS AND PROCEDURES

- Study procedures and their timing are summarized in the SoA.
- Adherence to the study design requirements, including those specified in the SoA, is essential and required for study conduct.
- The investigator is responsible for ensuring that procedures are conducted by appropriately qualified or trained staff. Delegation of study site personnel responsibilities will be documented in the Investigator Trial File Binder (or equivalent).
- All study-related medical decisions must be made by an investigator who is a qualified physician.
- All screening evaluations must be completed and reviewed to confirm that potential participants meet all eligibility criteria. The investigator will maintain a screening log to record details of all participants screened and to confirm eligibility or record reasons for screening failure, as applicable.
- Procedures conducted as part of the participant's routine clinical management (eg, blood count) and obtained before signing of ICF may be utilized for screening or baseline purposes provided the procedure met the protocol-specified criteria and were performed within the time frame defined in the SoA.
- Additional evaluations/testing may be deemed necessary by the investigator and or the Sponsor for reasons related to participant safety. In some cases, such evaluation/testing may be potentially sensitive in nature (eg, HIV, Hepatitis C), and thus local regulations may require that additional informed consent be obtained from the participant. In these cases, such evaluations/testing will be performed in accordance with those regulations.

The sample collection from each participant over the study is served to prove the efficacy and safety of the study intervention and will be described in laboratory manual.

Local laboratory use is allowed for the purpose of close monitoring of safety signals and should follow the site's clinical practice.

Repeat or unscheduled samples may be taken for safety reasons or for technical issues with the samples.

## **8.1 Administrative and General Procedures**

### **8.1.1 Informed Consent**

The investigator or medically qualified designee (consistent with local requirements) must obtain documented consent from each potential participant or each participant's legally acceptable representative prior to participating in a clinical study. If there are changes to the participant's status during the study (eg, health or age of majority requirements), the investigator or medically qualified designee must ensure the appropriate consent is in place.

#### **8.1.1.1 General Informed Consent**

Consent must be documented by the participant's dated signature or by the participant's legally acceptable representative's dated signature on a consent form along with the dated signature of the person conducting the consent discussion.

A copy of the signed and dated consent form should be given to the participant before participation in the study.

The initial ICF, any subsequent revised written ICF, and any written information provided to the participant must receive the Institutional Review Board/Independent Ethics Committee's (IRB/IEC's) approval/favorable opinion in advance of use. The participant or his/her legally acceptable representative should be informed in a timely manner if new information becomes available that may be relevant to the participant's willingness to continue participation in the study. The communication of this information will be provided and documented via a revised consent form or addendum to the original consent form that captures the participant's dated signature or by the participant's legally acceptable representative's dated signature.

Specifics about a study and the study population will be added to the consent form template at the protocol level.

The informed consent will adhere to IRB/IEC requirements, applicable laws and regulations, and Sponsor requirements.

### **8.1.2 Inclusion/Exclusion Criteria**

All inclusion and exclusion criteria will be reviewed by the investigator who is a qualified physician to ensure that the participant qualifies for the study.

### **8.1.3 Participant Identification Card**

All participants will be given a participant identification card identifying them as participants in a research study. The card will contain study site contact information (including direct telephone numbers) to be used in the event of an emergency. The investigator or qualified designee will provide the participant with a participant identification card immediately after

the participant provides written informed consent. At the time of intervention allocation/randomization, site personnel will add the treatment/randomization number to the participant identification card.

The participant identification card also contains contact information for the emergency unblinding call center so that a healthcare provider can obtain information about study intervention in emergency situations where the investigator is not available.

#### **8.1.4 Medical History**

A medical history will be obtained by the investigator or qualified designee.

#### **8.1.5 Prior and Concomitant Medications Review**

##### **8.1.5.1 Prior Medications**

The investigator or qualified designee will review prior medication use, including any protocol-specified washout requirement, and record prior medication taken by the participant within 12 weeks before the Visit 1. Please note that the prior medications for the treatment of hypercholesterolemia must be documented in eCRF.

##### **8.1.5.2 Concomitant Medications**

The investigator or qualified designee will record medication, if any, taken by the participant during the study.

#### **8.1.6 Assignment of Screening Number**

All consented participants will be given a unique screening number that will be used to identify the participant for all procedures that occur prior to randomization. Each participant will be assigned only 1 screening number. Screening numbers must not be re-used for different participants.

#### **8.1.7 Assignment of Treatment/Randomization Number**

All eligible participants will be randomly allocated and will receive a treatment/randomization number. The treatment/randomization number identifies the participant for all procedures occurring after treatment allocation/randomization. Once a treatment/randomization number is assigned to a participant, it can never be re-assigned to another participant.

A single participant cannot be assigned more than 1 treatment/randomization number.

Randomization number will be allocated at Week 0 (Visit 4) via IVRS/IWRS.

### **8.1.8 Study Intervention Administration**

Administration of first study dosing during randomization phase will be witnessed by the investigator and/or study staff at study site. Subsequent dosing will be performed once daily by the participant (i.e., unsupervised at his/her home). Since MK-0653C and atorvastatin differ in appearance thus corresponding matching placebos will be provided to ensure the efficient blinding. Participants who successfully pass the eligibility check at Visit 4 will be randomized within each cohort and will receive one bottle (20 mg atorvastatin or matching placebo) and one blister (MK-0653C or matching placebo) of study treatments during the double-blinded treatment period. Participants should be instructed to take 1 (for Cohort A) or 2 (for Cohort B) tablets from bottle and 1 tablet from blister every day during the study (i.e., Cohort A: either 1 tablet of MK-0653C 10/10 mg and 1 tablet of placebo matched to 20 mg atorvastatin OR 1 tablet of atorvastatin 20 mg and 1 tablet of placebo matched to 10/10 mg MK-0653C; Cohort B: either 1 tablet of MK-0653C 10/20 mg and 2 tablets of placebo matched to 20 mg atorvastatin OR 2 tablets of atorvastatin 20 mg and 1 tablet of placebo matched to 10/20 mg MK-0653C).

Participants will be provided with enough study treatment to last between study site visits.

#### **8.1.8.1 Timing of Dose Administration**

Administration of study medication will be performed once daily at approximately the same time each day for 12 weeks during the double-blinded treatment period, without regard to the time of meals.

#### **8.1.9 Trial Compliance (Medication/Diet/Activity/Other)**

Adherence to study treatment will be assessed by tablet count at Visit 4-6. Participants with  $\geq 75\%$  compliance during run-in period will be eligible for study entry.

Every effort must be made to maintain adherence to study treatment dosing per protocol as close to 100% as possible. Interruptions from the protocol specified treatment plan for compliance  $< 75\%$  require consultation between investigator and Sponsor.

Participant will be instructed for prohibited medication according to the protocol exclusion criteria. And also participant will be instructed for diet, or a similar diet and life style according to China 2016 Guideline at Visit 1. Investigator will check any changes at each visit regarding concomitant medication, diet and life style, and document the changes on eCRF dedicated page.

